6.2.3. Cost Endpoints

We will employ a health care perspective in this RCT and calculate the costs of all services

associated with care, regardless of who bears the cost. These costs will include the direct costs of medical care, the costs of non-medical care and indirect health care costs. The investigators will identify those costs that are related to the research protocol and are not part of usual care. We will conduct the economic analysis in the cohort of U.S. patients, with an expected sample size of 500 patients.

6.2.3.1 Direct Costs of Medical and Non-Medical Care

We will derive costs by using the clinical dataset to identify the resources that patients use during the course of the trial, and then assign payments/prices for each resource used. There are a multitude of payers in the U.S. that reimburse for services at different rates. We propose to use the Medicare payments as representative rates. For inpatient hospital days, we will use the Medicare reimbursement for the DRG codes assigned on the patient's discharge. We will not include physician time in our costing, as it is a much smaller part of the overall costs and it requires substantial data collection efforts to capture. For those patients who need nursing facilities or long-term institutional care, we will use the National Medicare average allowed daily rate to impute payments. The use of services outside the study hospitals, such as emergency room visits, out of network hospitalizations, nursing home care, and rehabilitative facility care will be determined by a structured questionnaire administered by site coordinators to all enrolled patients.

In seeking medical treatment, patients may also incur significant non-medical care costs. These costs may include the value of unpaid care provided by family members and friends, the costs of uncompensated home health care and the "costs" of time dedicated to care by the patient. We will focus on obtaining the value of unpaid care provided by family and friends with the following question administered at 6 month intervals by site coordinators on the Patient Encounter form (AR14): Has your illness required any members of your family or friends to restrict their work or social activities? If yes, about how many hours per week have friends or family spent in helping with your care? Each hour of care will be valued at an average hourly total compensation rate for civilian workers as reported in the base year by the Bureau of Labor Statistics. The value of home health care will be determined by asking patients directly if they had a home health aid or home nurse and the number of hours per week that they are employed. The hourly wage rate will be determined by the average Medicare reimbursement rate. We will not collect data on travel costs or the amount of time patients must spend seeking treatment (i.e. the opportunity cost of lost leisure time as measured by the wage rate), because of the substantial burden involved in such data collection.

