5.2 Interventional Therapy (Refer to Manual of Procedures)

A patient randomized to interventional therapy is expected to begin interventional therapy within 3 months following randomization. Interventional therapy consists of endovascular attempts at occlusion of the nidus and feeding vessels, coiling or microsurgery for feeding artery aneurysms, microsurgery for BAVM itself, and radiosurgery, these alone or in various combinations and timings.

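### The costing promises all services but leaves out physician time; because procedural physician services fall mainly in the interventional arm, the cost difference between arms is probably understated

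*Protocol*

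**What the plan says.** Protocol section 6.2.3 (Cost Endpoints) sets the scope: "We will employ a health care perspective in this RCT and calculate the costs of all services", and continues "associated with care, regardless of who bears the cost". The next sentence lists direct medical, non-medical and indirect health care costs as components.

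Section 6.2.3.1 gives the method. Resources are found by "using the clinical dataset to identify the resources that patients use during the course of the trial", and each is then given a price, with Medicare payments as the representative rate. On hospital stays it says: "For inpatient hospital days, we will use the Medicare reimbursement for the DRG codes assigned on the patient's discharge". The exclusion follows directly: "We will not include physician time in our costing, as it is a much smaller part of the overall costs". A second reason is that "it requires substantial data collection efforts to capture". No other line of the two sections prices physician services.

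On unpaid help, the same section says: "We will focus on obtaining the value of unpaid care provided by family and friends". Those hours are asked for every 6 months and valued at an average compensation rate.

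The result feeds item 5 of section 1.2 (Secondary Aims): the cost of each treatment, and the cost-effectiveness implications if medical management is not superior but also not inferior.

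**The concern.** The scope statement and the exclusion cannot both stand. A reader of the eventual economic report would take the total to cover all services, when a whole class has been left out.

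The more important question is whether the omission cancels between arms. Section 5.2 states: "A patient randomized to interventional therapy is expected to begin interventional therapy within 3 months following randomization". That treatment is endovascular, microsurgical or radiosurgical, alone or combined. Under the Précis (Interventions and Duration), the medical arm receives pharmacological therapy and becomes a candidate for the same procedures only after a hemorrhage or infarction. A component that is planned for one arm and contingent in the other does not drop out of a difference. Leaving it out makes intervention look less expensive, relative to medical management, than it is.

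The protocol itself fixes this exclusion, so it is not a detail left open for a statistical analysis plan.

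**Working it through.** **Step 1. Reproduce the plan's own figures.** Section 2.1 gives nearly 3,000 U.S. cases a year at $50,000 to $100,000 each. 3,000 × $50,000 = $150 million and 3,000 × $100,000 = $300 million, as stated. The hypotheses text in section 1 assumes a 5-year event rate of 20% under intervention and a hazard ratio of 0.60, so the medical-arm rate is 1 − 0.80^0.60 = 12.5%. This matches the stated absolute reduction of 7.5%. These checks confirm the inputs only; the protocol states neither a physician share nor a cost difference between arms.

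**Step 2. How unequal are procedural physician services?** Let x be the fraction of the medical arm later treated. Assume every interventional patient is treated and a later procedure costs the same. The interventional arm's share of procedural physician cost is then 1/(1 + x). If every medical-arm patient with an event were treated:

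- 5% event rate (best natural history, section 2.2): 1/1.05 = 95%
- 12.5% (design assumption): 1/1.125 = 89%
- 20% (worst medical-management figure, section 2.2): 1/1.20 = 83%

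The endpoint includes death, so not all event patients could be treated; on the other hand, follow-up runs to 7.5 years.

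**Step 3. Add routine physician care in both arms.** Section 5.1 gives participants medical management, so procedures are not the whole of physician cost. Assume equal routine care of m per patient, C = $75,000 (midpoint of the stated range), x = 12.5% and procedural physician cost P = C × s, where s is the physician share. The interventional share of all physician cost is (P + m)/(P + m + 0.125P + m).

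- s = 5%, m = $5,000: P = $3,750; 8,750/14,218.75 = 62%
- s = 30%, m = $1,000: P = $22,500; 23,500/27,312.5 = 86%

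So the arms are unequal, but the medical arm's part is not negligible.

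**Step 4. Illustrate the effect on the difference.** Equal routine care cancels, leaving an omitted amount of C × s × (1 − x) per patient. The share s is **not in the protocol**; 5% to 30% is an assumption.

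| s | C = $50,000; x = 0 / 12.5% / 20% | C = $100,000; x = 0 / 12.5% / 20% |
|---|---|---|
| 5% | $2,500 / 2,188 / 2,000 | $5,000 / 4,375 / 4,000 |
| 10% | $5,000 / 4,375 / 4,000 | $10,000 / 8,750 / 8,000 |
| 20% | $10,000 / 8,750 / 8,000 | $20,000 / 17,500 / 16,000 |
| 30% | $15,000 / 13,125 / 12,000 | $30,000 / 26,250 / 24,000 |

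The amount is positive for any x below 1. The sign could reverse only if medical-arm patients used more routine physician care than interventional patients by more than the amount shown, which is $2,000 at the low end. That is why the direction is probable rather than certain.

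**Step 5. Test the two stated reasons.** The small-share reason concerns the total and has no figure behind it; the aim needs the difference, which depends on the imbalance in steps 2 and 3. The burden reason would apply to measuring minutes, but the chosen method multiplies recorded resources by payments. Sections 5.2.1 and 5.2.3 put embolization and radiotherapy details on form AR13. Section 5.2.2 (microsurgery) does not name that form, but the section 7.1 schedule has event-driven Interventional Therapy and Hospitalization forms, and an encounter form at follow-up contacts and after each intervention.

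**The case against.** The exclusion is declared openly and with reasons, as are those of travel costs and patient time. It touches one secondary aim and neither the primary endpoint, the error rate nor the sample size. It also works against the trial's own hypothesis, because it understates any saving from medical management. If medical management were non-inferior and already cheaper without physician costs, adding them would only strengthen that result. A conclusion could change mainly if intervention proved better or the totals were close. All of this stands and limits the weight of the point, but it does not remove the mismatch in scope or the imbalance between arms.

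A reader might infer that nearly all physician cost sits in the interventional arm and almost none in the medical arm. The protocol does not support that: section 5.1 gives physician-led care to medical-arm patients, and the Précis allows them later procedures. A reader might also want a dollar total for the trial. None can be given, because the physician share is unknown and the $50,000 to $100,000 in section 2.1 is a background figure with no breakdown, so one cannot tell whether it includes professional fees.

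Reading physician time as physician services is an interpretation. It is a reasonable one, since nothing else in the costing prices those services.

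Finally, it is tempting to say that adding unpaid family care breaks the health care perspective. Section 6.2.3 expressly lists non-medical costs, so unpaid care is a declared component and what remains is mainly a matter of labelling.

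**Conclusion.** The point holds in limited form. Sections 6.2.3 and 6.2.3.1 contradict each other on scope. Procedural physician services fall mainly in the interventional arm (83% to 95% in step 2), so the interventional-minus-medical cost difference is probably understated.

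The size cannot be established from the protocol. The $2,000 to $30,000 per patient is an illustration resting on an assumed physician share of 5% to 30%, on 0 to 20% of the medical arm being treated later, and on equal routine physician care in both arms. The consequence is confined to secondary aim 5. It is worth correcting because the remedy is cheap and the cost result is meant to inform a choice between the two strategies.

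**What to change.** Replace the exclusion in section 6.2.3.1 with a rule along these lines:

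> In both arms, physician services for each interventional procedure, hospitalization and physician visit recorded on study forms will be valued at national Medicare physician payment rates. The cost difference between arms will be reported with and without this component. Physician care not captured on study forms remains unpriced.

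Narrow the all-services wording in section 6.2.3 to match. Covering recorded visits as well as procedures and hospitalizations matters: pricing only the latter two would leave outpatient physician care out, and that remaining gap could weigh more on the medical arm.

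As a minor addition, report the total with and without unpaid family care, so that one figure fits the health care label and the other the broader scope already declared.

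The cost is some work mapping recorded procedures to payment categories, since the protocol mentions no billing or procedure codes on the therapy form. Restricting the rule to items already on study forms avoids new data collection from patients, and no physician needs to be timed.

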7.1 DATA COLLECTION SCHEDULE

Study Visit (months after randomization) (V)=Visit, (P)=Phone Call	Screening / Baseline	6 (V)	12 (V)	18 (V)	24 (V)	30 (P)	36 (V)	42 (P)	48 (V)	54 (P)	60 Month Visit (V)	66 (P)	72 (V)	78 (P)	84 (V)	End of Study (V or P)		Event Driven
																(V)	(P)	
Window (days)	0	±30	±30	±30	±30	±30	±30	±30	±30	±30	±30	±30	±30	±30	±30	±30	-30	
Informed Consent	X																	
Release of Medical Information	X																	
HIPAA Authorization (US only)	X																	
Demographics	X																	
Eligibility Evaluation	X																	
Randomization	X																	
Image Study	X																	
Presentation History	X																	
AVM Morphology	X																	
Rankin Scale	X [#]	X	X	X	X	X	X	X	X	X	X	X	X	X	X	X	X	X [*]
NIH Stroke Scale	X	X	X	X	X		X		X		X		X		X		X	X [*]
Medical History	X																	
Medications	X	X	X	X	X	X	X	X	X	X	X	X	X	X	X	X	X	
Quality of Life: SF-36	X	X	X	X	X		X		X		X		X		X		X	
Quality of Life: Euroqol	X	X	X	X	X	X	X	X	X	X	X	X	X	X	X	X	X	
Interventional Therapy																		X
Delayed Treatment																		X
Patient Encounter		X	X	X	X	X	X	X	X	X	X	X	X	X	X	X	X	X ^{&}
Adverse Event																		X
Hospitalization																		X
Mortality																		X
Missed Visit																		X
Voluntary Withdrawal																		X
60 Month Visit											X [^]							
End of Study																	X	
Investigators Statement																	X	

* collected following each BAVM interventional therapy, all neurological adverse events and hospitalization

& collected following each BAVM interventional therapy

[^] window of -6 months for image study

[#]if Rankin scale collected more than 6 months prior to randomization, assessment should be repeated
